The U-s National Athletic Injury Reporting System (NAIRS) divides overuse injuries into the following categories:

- a) Undetectable – where the athlete does not stop their athletic activities,
- b) Minor leaving 1-7 days of sports activity
- c) Moderate: from 8 to 21 days of abandonment of activities and
- d) Major: more than 21 days of loss of activities and serious injuries, resulting in permanent disability.

TREATMENT OF KNEE OVERUSE SYNDROME:

There is no specific treatment guideline for most conditions caused by knee overuse. It is essential to have an adequate diagnosis of osteoarthritis at an early stage to incorporate the most appropriate treatment. The most recommended treatment for early osteoarthritis, includes weight loss, physical therapy, non-steroidal anti-inflammatory drugs, nutraceutical supplements, topical treatments, and steroid injections. In knee overuse syndrome, starting with a decrease in overload, correcting gait abnormalities, improving training techniques, adding strengthening and stretching exercises, as well as adapting the use of footwear and adding physical therapies with ice, have resulted effective methods as first line treatment.

NON-SURGICAL

The first line of treatment in early osteoarthritis of the knee caused by overuse in sports should be given conservatively and without surgery. The main objective of this treatment is to delay arthroplasty through a protocol that includes non-steroidal anti-inflammatory drugs, joint injections, as well as general measures of weight loss following a series of low-impact exercises. Physical therapy has an important role in the treatment of early osteoarthritis in athletes, stretching the extensor and abductor muscles of the knee can reduce pain and improve function. Cold therapy can also decrease the level of prostaglandins in synovial tissue resulting in decreased inflammation, reducing atherogenic muscle inhibition and facilitating vastus medialis motor neuron activity. Cryotherapy may allow more effective strengthening of the quadriceps in patients with knee joint abnormality; therefore, despite the current lack of clear research evidence, cryotherapy is recommended as a mainstay of conservative treatment in physiotherapy.

NON-STEROID ANTI-INFLAMMATORY AGENTS

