Drug treatments commonly include the use of pain relievers such as aspirin or acetaminophen, and nonsteroidal anti-inflammatory drugs (NSAIDs); The use of NSAIDs is controversial due to the absence of histological inflammatory response in knee overuse syndrome. There is also concern that NSAIDs may interfere with the normal healing response of muscles and tendons.

INFILTRATIONS

- Platelet Rich Plasma (PRP) injections have been studied for the treatment of tendinopathy and osteoarthritis, obtaining Good medium-term results in the treatment of recalcitrant patellar tendinopathy by applying multiple injections. The use of PRP has been qualified by the Clinical Practice Guidelines of the American Academy of Orthopedic Surgeons (AAOS) for the treatment of knee osteoarthritis, however their decision was that it's use cannot be recommended for or against treatment of knee osteoarthritis.

INFILTRATION WITH HIALURONIC ACID

Visco-supplementation with hyaluronic acid is one of the most recommended treatments for the non-surgical management of osteoarthritis, it can be recommended as first-line therapy, or when corticosteroids and non-steroidal anti-inflammatory drugs are inefficient, contraindicated or poorly tolerated; viscosupplementation is a safe procedure, without any systemic or local side effects, excluding possible injection pain and a feeling of heaviness for a few hours or days after treatment. Hyaluronic acid is one of the most used methods to preserve the cartilage and intra-articular structures of the knee. It protects the chondrocytes and lubricates the joint to stabilize the cartilage and the synovial membrane, benefits have also been described in its analgesic and intra-articular structures of the knee. It protects the chondrocytes and lubricates the joint to stabilize the cartilage and the synovial membrane, benefits have also been described in its analgesic and anti-inflammatory effects. Viscosupplementation significantly reduces knee pain during the first months, after which the effect is maintained for another 12 to 18 months. During this time joint function can improve and therefore patients can quickly return to sports activities.

Physiotherapy

A fundamental part of the overuse syndrome treatment is to know that mistakes in techniques of training could be avoided by guidelines of different type of exercises. Physical therapy should focus on stretching inflexible muscles and tendons (for

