To evaluate safety and efficacy of hyaluronic acid with sorbitol in athletes with overuse knee pain by comparing functional outcomes at short, medium and long term after treatment.

Specific Objectives

- To assess the safety and efficacy of hyaluronic acid with sorbitol in patients with sports-associated knee pain.
- To compare the clinical and functional results of patients with sport-associated knee pain after before and after treatment.

METHODS

Study Design

This research will be a cohort study, prospective and unidirectional direction.

Selection Criteria

- Patients with knee pain for more than 3 months
- Patients between 30 and 55 years old
- Patients without a history of previous knee joint surgery.
- Patients without chronic-degenerative diseases such as diabetes, hypertension, rheumatoid arthritis or other autoimmune diseases.
- Patients who perform impact social sports at least 3 times a week for more than 1 hour in the last 3 months prior to treatment.
- Patients without a history of allergies to non-steroidal anti-inflammatory drugs.
- Patients with no history of infection in or around the knee.

EXCLUSION CRITERIA

- Patients who cannot be categorized as social athletes.
- Patients with an associated sports injury that limits their sports practice.
- Patients who have a treatment associated with knee pain independent of that established in the study protocol.

ELIMITATION CRITERIA

- Patients who suffer from an injury or illness during the study that may limit their sports activity or who require an analgesic or anti-inflammatory treatment other than that established in the protocol.
- Patients who personally want to leave the study.
- Patients who did not have complete follow-up during the study.
- Patients who present an allergic or infectious reaction related to hyaluronic acid or prolotherapy or sepsis and antisepsis methods for infiltration.
- Patient with an allergic reaction to non-steroidal anti-inflammatory drugs.

VARIABLES

Variable	Operational Definition	Dimension	Variable type	Instrument	Indicator
Age	Time of life of any person	Without categories	Quantitative Discrete	Interview	Years
Gender	Biological and physiological characteristics that differentiate a man from a woman	Female Male	Qualitative Nominal	Interview	Gender
Body Mass Index	Score calculated by weight and height of a person.	Normal Overweight Obesity	Quantitative Discrete	Measuring tape Weighing machine	Weight in kg / Height in square meters

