Affected Knee	Anatomic Knee side	Left	Qualitative	Physical Exploration	Left

		Right	Nominal		Right
Athlete	Person who practice any type of sport	Social Amateur Professional	Qualitative Nominal	Interview	Have a sports activity for more than 3 months, 3 times a week over 60 minutes per session
Score KOOS	Scores that evaluate functional and osteoarthritis around the knee	Symptoms Joint Stiffness Pain Regular activities Sports activities Quality of life	Quantitative Discrete	Interview Physical Exam	Percentage 0-100%
Score IKDC	International Knee Documentation Committee	Symptoms Regular Activities Sports Activities	Quantitative Discrete	Interview Physical exam	Percentage 0-100%
Visco supplementation	Intraarticular joint injection of high weight molecular hyaluronic acid with sorbitol	Mono dose Multi dose	Qualitative Nominal	Hyaluronic acid 2ml plus sorbitol 2 dose per knee	Yes = Knee joint infiltration No= Did not apply
Training sports technique	Coaching for adequate techniques of certain sports	Manual technique Instrumented	Qualitative Nominal	Personalized coaching techniques	Achievement survey

	activities			Or Information brochure	
--	------------	--	--	----------------------------	--

Research Universe

General Population who does sports activities and have knee overuse syndrome between June of 2022 and October 2022.

Sample Size

It will be a non-probability sampling where will be chosen participants who meet selection criteria over the enrolling time which will be for 5 months. The lower limit will be 60 participants and the higher limit will be 120 participants.

Sample size formula: $n(\text{sample})$, z (confidence level), p (probability to occur the studied event), q (probability to didn't occur the studied event) and e (maximum accepted estimated error)

$$Z^2 * p*q$$

$$n = \frac{Z^2 * p*q}{e^2}$$

Study Design

Research enrolling and diffusion will be initiated after authorization of the ethics and investigation committee. All participants with knee pain related to sports will be accepted for a physical evaluation. All participants will be interviewed about physical activities, sports, injuries, and knee pain. Once they have been categorized as athletes with knee overuse pain syndrome and have met the selection criteria, then will be invited to the research. For this, the participants must be agreed and sign the informed consent Appendix 1 and 2.

Before treatment Group

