To participants who initiate the study research will be applied the KOOS and IKDC scores, the results will be recorder in the collection data sheet. Appendix 2. Participants will be explored by physical exam focus on knee pathology, and also an echography knee scan

looking for non-overuse pain injuries. Coaching for sports activities will be explained for each patient in order to improve its own training techniques adding stretching exercises for previous and after training.

After treatment Group

After KOOS and IKDC scores were recorded two doses of Hyaluronic Acid plus sorbitol will be applied. Technique: On the examination table, the patient will lie down at supine position and the area of the knees to be infiltrated will be discovered. Asepsis of the knee region will be performed using an iodine and alcohol solution, the remaining synovial fluid in the joint will be extracted with a 10cc syringe then 4 milliliters of 80 mg of hyaluronic acid plus 160 mg of sorbitol will be applied (Synolis VA Aptissen S. A.) at the sub quadriceps level with a 22G x 32mm sterile needle. At the end of the infiltration, the needle will be removed, and the injection site will be covered with a small sticky-band, which can be thrown away after 20 minutes. It will be recommended to not make any kind of sports activity following the next 72 hours and apply ice therapy 3 times per day for over 20 minutes. Scores recorded data will be made at 15 days, then at 3 and 6 months.

Once the enrolling phase of the trial is concluded, statistical analysis will be made with Excel Office software for Windows, IBM SPSS and Prism.

Statistical analysis

Recorded data of the functional scores will be evaluated before and after treatment, also at 15 days, 3 and 6 months after hyaluronic acid supplementation.

Data analysis will be made by means standard deviation for numeric variables, also t-test for parametric and Wilcoxon Mann Whitney for non-parametric variables, a standard error of 95% is allowed. Differences in time will be calculated and group compared by Anova test. Variable correlation and association measures with relative risk and attributable risk with Fisher's test will be made with a confidence interval of 95%.

Ethical Implications

This research project will be developed after approval of the ethics and research Institutional committee.

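### Eliminating injected participants who need other pain medication or miss follow-up selects on a post-injection event and is expected, not certain, to raise the before/after change

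*Combined protocol and SAP*

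**What the plan says.** **Elimination criteria (Methods).** The first bullet has two limbs. One is an injury or illness during the study that may limit sport. The other covers participants who "require an analgesic or anti-inflammatory treatment other than that established in the protocol". A separate bullet eliminates "Patients who did not have complete follow-up during the study". The term elimination is not defined.

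**Care in the protocol (Before treatment Group, After treatment Group).** Participants receive the hyaluronic acid and sorbitol injection, coaching and stretching exercises. They are advised to avoid sport for 72 hours and to "apply ice therapy 3 times per day for over 20 minutes". No analgesic or anti-inflammatory drug is named. However, the selection criteria ask for "Patients without a history of allergies to non-steroidal anti-inflammatory drugs", and an allergic reaction to such a drug is itself an elimination criterion.

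**Measurement and analysis.** "Scores recorded data will be made at 15 days, then at 3 and 6 months". Both scores run from 0 to 100, and higher is better. The Statistical analysis section compares scores before and after treatment in one cohort, using means and standard deviations, t-test or Wilcoxon Mann-Whitney, and ANOVA over time. It states no analysis set, no method for missing scores, no rule for scores obtained after rescue medication, and no sensitivity analysis.

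**The concern.** Both criteria act on events after the injection. The condition under study is knee pain and KOOS has a pain subscale, so a participant who needs further pain medication is plausibly someone for whom the injection worked less well. If such participants leave the analysis, the mean is taken over those who did not need help. With no comparator, nothing shares or cancels the loss.

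The incomplete-follow-up criterion can only be settled at the end of a participant's six months. Someone with good 15-day and 3-month records who misses the last visit would be eliminated in retrospect. This suggests that whole records go, which would alter the 15-day result as well as the later ones.

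If eliminated participants are in fact kept, the plan has the opposite gap: it does not say how to treat scores improved by other medication. At stake is the study's central claim of good clinical and functional results, which rests on an uncontrolled mean change.

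**Working it through.** **No figure to reproduce.** The documents give no expected elimination rate, mean change, standard deviation or rescue effect. The only related number is the planned size of 60 to 120 (Sample Size). Every input below other than that range is an assumption.

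**Step 1: removal against the change without rescue.** Let f be the share removed, R the mean change of those retained, and x the mean change that those removed would have had without rescue.

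- Mean for all injected, without rescue: (1 − f)R + f·x
- Mean after removal: R
- Shift: f(R − x), the share removed times the shortfall

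At f = 15% (9 of 60, leaving 51; or 18 of 120, leaving 102):

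- shortfall 0: shift 0
- shortfall 5: 0.15 × 5 = 0.75
- shortfall 12: 0.15 × 12 = 1.8
- shortfall 20: 0.15 × 20 = 3.0
- those removed did 5 points better: 0.15 × (−5) = −0.75

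If whole records are dropped, a smaller assumed 15-day shortfall of 0 to 5 points gives 0 to 0.75 at that visit.

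**Step 2: removal against the change regardless of later treatment.** Let rescue add g points to the scores of those who take it.

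- As-observed mean for all injected: (1 − f)R + f(x + g)
- Removal minus as-observed: f(R − x − g) = f(shortfall − g)

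The sign changes where the shortfall equals the gain from rescue.

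**Step 3: worked cases.** Assume f = 15%, R = 15 and g = 10. Setting post-rescue scores to baseline gives 0.85 × 15 = 12.75 in every row.

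| x | Shortfall | Mean without rescue | As-observed mean | Removal minus without rescue | Removal minus as-observed | Baseline carried minus without rescue |
|---|---|---|---|---|---|---|
| −5 | 20 | 12.0 | 13.5 | +3.0 | +1.5 | +0.75 |
| 0 | 15 | 12.75 | 14.25 | +2.25 | +0.75 | 0 |
| +3 | 12 | 13.2 | 14.7 | +1.8 | +0.3 | −0.45 |
| +15 | 0 | 15.0 | 16.5 | 0 | −1.5 | −2.25 |
| +20 | −5 | 15.75 | 17.25 | −0.75 | −2.25 | −3.0 |

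In every row the as-observed mean exceeds the mean without rescue by f·g = 0.15 × 10 = 1.5. The first row also shows that carrying baseline forward is not a lower bound: when those rescued would have got worse, it lies 0.75 above the mean without rescue.

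**The case against.** **Direction.** A reader might infer that the rule necessarily inflates the result. It does not. The second limb is not restricted to knee pain, so a tablet for a headache would count, and it shares a bullet with intercurrent injury and illness. The more that removals come from such causes, the nearer the shift is to zero; if good responders are removed, it reverses. Against the as-observed mean, which is the analysis proposed below, removal understates whenever the shortfall is less than the rescue gain. This objection stands, and it limits the claim to an expected direction against one stated comparison.

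**Size.** Taking 5% to 30% removed and a shortfall of −5 to 20 points, the shift in Step 1 runs from 0.30 × (−5) = −1.5 to 0.30 × 20 = +6.0. A reader might take +6.0 as the likely bias. It needs both extremes together, neither is documented, and it is not measured against the as-observed mean.

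**Breadth.** The background says that "stretching the extensor and abductor muscles of the knee can reduce pain and improve function", and of hyaluronic acid that "benefits have also been described in its analgesic and anti-inflammatory effects". A reader might infer that the rule reaches physiotherapy, platelet-rich plasma or a repeat injection. The documents do not support that. Stretching is part of protocol care, and the background treats anti-inflammatory drugs under a heading separate from infiltrations and physiotherapy. The rule should be read as covering medication.

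**An allowed drug.** The allergy criteria suggest that an NSAID may have been intended as protocol care, and the data sheet in Appendix 3 stops at its treatment heading in the supplied text. An allowed NSAID would narrow the rule, so it cannot be said that every analgesic triggers elimination.

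**Meaning of elimination.** Removal from the analysis, and loss of the 15-day score with it, is inferred. The Statistical analysis section refers to recorded scores without limiting them to completers. But it offers no other set, and if these participants are kept there is no rule for their scores after rescue. Either way a statement is missing.

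**Conclusion.** The concern holds in a limited form. As written, the plan selects on post-injection events, one of which is a plausible marker of poor response, and a single-group design has nothing to offset that. The mean KOOS or IKDC change is expected, not certain, to be higher than for all injected participants without rescue: by 0 to 3.0 points if 15% are removed with a shortfall of 0 to 20 points. Measured against the change regardless of later treatment, with an assumed rescue gain of 10, the same 15% gives 0.15 × (0 − 10) = −1.5 to 0.15 × (20 − 10) = +1.5.

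The conclusion rests on elimination meaning removal from analysis, on need for medication being linked to poorer response, and on inputs that the documents do not supply. It should be corrected because the remedy is cheap and the rule bears on the main result; no particular size of bias has been shown.

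**What to change.** 1. Amend the analgesic/anti-inflammatory and incomplete-follow-up criteria so that neither removes a participant's recorded scores from the analysis. State whether any NSAID is allowed.
2. Make the main analysis all injected participants with a baseline score, using every available score at 15 days, 3 and 6 months, and label it as the change regardless of later treatment.
3. Pre-specify one sensitivity analysis that sets post-rescue scores to baseline (no improvement), described as a conservative check and not as a bound.
4. Report the number rescued or eliminated, by visit and reason.

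Where follow-up is still open, record the type, date and side of rescue if the data sheet does not already do so. The "Mono dose Multi dose" dimension in the Variables table might show a repeat injection but would not capture medication.

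Timing matters. The document is dated 01/12/2023, and the population is defined for June to October 2022. Six months after October 2022 is April 2023, so on a day/month reading of the date, planned follow-up would already be over. Items 2 to 4 can still be done then, with recorded data where available.

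The cost is a short amendment to two criteria, possibly one follow-up item, and one extra analysis. The reported benefit may change and could be smaller, and the main analysis will include any gain from rescue.

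### Safety is a stated objective, but the plan specifies no adverse-event variable, safety set or event summary, and does not say how elimination for a related reaction affects the analysis

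*Combined protocol and SAP*

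**What the plan says.** Safety appears in the study title, the aims in the Abstract and the Justification. The General Objective begins "To evaluate safety and efficacy of hyaluronic acid with sorbitol in athletes with overuse knee pain by comparing functional outcomes", and the first Specific Objective is "To assess the safety and efficacy of hyaluronic acid with sorbitol in patients with sports-associated knee pain".

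The Variables table lists age, gender, body mass index, affected knee, athlete category, KOOS, IKDC, viscosupplementation and training technique. Under After treatment Group, what is scheduled after the injection is score recording at 15 days, 3 months and 6 months. The Statistical analysis section evaluates the functional scores. It adds relative risk, attributable risk and Fisher's test, but names no event, exposure or comparator, and it defines no analysis set.

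The Elimination criteria include "Patients who present an allergic or infectious reaction related to hyaluronic acid or prolotherapy or sepsis and antisepsis methods for infiltration". The same list holds "Patients who personally want to leave the study" and "Patients who did not have complete follow-up during the study". Nothing states whether elimination ends treatment, follow-up or membership of the analysed set.

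The background section on hyaluronic acid infiltration describes viscosupplementation as free of side effects, "excluding possible injection pain and a feeling of heaviness for a few hours or days after treatment". Neither of those two effects becomes a study variable.

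**The concern.** A stated objective needs something measured, a population to count it in and a summary to report. For safety the plan specifies none of the three. The only measure it links to safety is the functional scores.

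The one place where the methods mention reactions to the product or procedure is a list of reasons to eliminate the participant. A later statement that no allergic or infectious reaction occurred among analysed participants could therefore come from the product or from the rule, and a reader could not tell which. The Justification calls the existing evidence on safety in athletes limited, so a conclusion from this study may well be relied on.

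**Working it through.** **1. What the scores can and cannot show.** KOOS and IKDC (Appendices 1 and 2) ask about pain, stiffness and swelling, so a worsening score is a crude tolerability signal. Neither can identify an allergic or infectious reaction or attribute an event to the injection. Timing also matters, taking 15 days as counted from the injection:
- The IKDC items on pain frequency and on stiffness or swelling look back four weeks. At day 15 that covers the injection, but also 28 − 15 = 13 days before it.
- The KOOS items on degree of pain look back one week, so at day 15 they miss about the first 15 − 7 = 8 days.

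**2. The two readings of elimination.**
- The incomplete follow-up criterion suggests removal from the analysed set. On that reading, every participant with a related allergic or infectious reaction leaves the set, and a rate computed in it has numerator 0.
- The criterion on wishing to leave suggests only that participation ends. On that reading the data may be kept, but no planned analysis reports the reactions.

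The documents do not settle which applies. Neither reading gives a planned safety result.

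**3. The plan's own figures.** Sample Size gives a range of 60 to 120 participants beside a formula for a proportion, n = Z²pq/e². No values are given for p, q or e, and the event studied is not named. The range cannot be reproduced, and nothing ties it to an adverse event.

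**4. One illustration.** The count of 3 reactions is an assumption; the documents give no reaction rate. n = 60 is the plan's lower limit, and nobody else is assumed to be eliminated. Limits are Clopper-Pearson, two-sided 95%.
- All injected: 3/60 = 5.0%. Lower limit = Beta quantile(0.025; 3, 58) = 0.0104. Upper limit = Beta quantile(0.975; 4, 57) = 0.1392. The interval is 1.0% to 13.9%.
- After removal: 60 − 3 = 57 remain, so 0/57 = 0%. Upper limit = 1 − 0.025^(1/57) = 0.0627, or 6.3%.

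The 6.3% limit still covers 5.0%. The damage is to the point estimate, which is fixed at zero; the interval does not exclude the observed rate.

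**5. What an honest zero would show.** With complete follow-up of everyone injected, the upper limit is 1 − 0.025^(1/60) = 0.0596 (6.0%) for 0/60 and 1 − 0.025^(1/120) = 0.0303 (3.0%) for 0/120.

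**The case against.** The strongest reply has four parts.

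- **An event count may be obtainable.** The available data sheet (Appendix 3) stops at its treatment heading, and an adverse-event field may follow. The elimination criterion also presupposes that someone detects a reaction and judges it related, so the number eliminated for this reason could be reported. This stands. A reader might infer that the plan cannot yield any adverse-event rate; the documents support only that none is specified. A field would still not supply a safety set or a reporting rule.
- **The criterion may never operate.** At an assumed true rate of 1%, the chance of at least one reaction is 1 − 0.99^60 = 45% with 60 participants and 1 − 0.99^120 = 70% with 120. This also stands, so the point rests on the missing safety analysis and the undefined rule, not on the size of the illustration.
- **The research question and hypotheses are clinical and functional only.** True, so no safety test is called for. Safety remains an objective, and descriptive reporting is the least it needs.
- **Relative risk, attributable risk and Fisher's test could be applied to events.** With no named event and no stated comparator in a single treated cohort, that sentence is not a safety summary.

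A reader might also infer that other elimination criteria hide further harms of the product. The documents do not establish this. One criterion is "Patient with an allergic reaction to non-steroidal anti-inflammatory drugs", but After treatment Group describes rest from sport and ice and names no such drug. The injury or illness criterion is confined to conditions that may limit sport. The clause "who require an analgesic or anti-inflammatory treatment other than that established in the protocol" could catch someone whose injection pain led to such treatment, but that is only a possibility.

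**Conclusion.** The point holds. Followed as written, the plan would judge safety from functional scores, while participants with related allergic or infectious reactions meet an elimination criterion of undefined effect. That does not support a safety conclusion.

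The size depends on what elimination means. If it means removal, an assumed 5.0% becomes 0%. If it means only the end of participation, the loss is that no report is planned. A reader might infer that participants with reactions are certainly dropped from the analysis, but the text does not say so. The absence of a specified safety set and event summary depends neither on that reading nor on what the rest of the data sheet contains.

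**What to change.** 1. Define the safety set as everyone who received any injection. State that elimination, for any reason, never removes a participant or an event from it. How eliminated participants' scores are handled is a separate decision, to be stated with a reason.
2. Do not use functional scores as the only measure of safety. Report descriptively the number and percentage of all injected participants with any event, any related event, and any allergic or infectious reaction. Give exact 95% confidence intervals and the number followed to each contact, so that those lost early are not silently counted as event-free. If none occur, report the upper limit as in step 5 of the working.
3. Report the number of eliminations and the reason for each.
4. If the full data sheet has no adverse-event field, add one covering type, knee, onset, severity, relation and outcome. Where contacts are over, fill it from existing records and label it retrospective.

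The cost is wording, one table and possibly six data items. Much of the capture may have to be retrospective. Research Universe places the population between June and October 2022, and the document is dated 01/12/2023. If enrolment ran as stated, the 15-day contacts were over on either reading of that date, and the 6-month contacts (due by about April 2023) were over too if it means 1 December. Retrospective records may be incomplete, and the reported reaction rate may no longer be zero. No safety hypothesis test and no clinical rule is proposed.

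### Safety is an objective, but no harm variable or safety analysis is listed and the named injection reactions are elimination grounds: if only those kept are analysed, their rate is 0% whatever happened

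*Combined protocol and SAP*

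**What the plan says.** All references are to the combined protocol and SAP.

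- **Objectives.** Safety is in the study title and the general objective. The first specific objective reads "To assess the safety and efficacy of hyaluronic acid with sorbitol in patients with sports-associated knee pain". The general objective would judge safety and efficacy together, by comparing functional outcomes.
- **Variables.** The table has nine rows: age, gender, body mass index, affected knee, athlete category, KOOS, IKDC, viscosupplementation and training technique. The outcome rows are KOOS ("Scores that evaluate functional and osteoarthritis around the knee") and IKDC, both quantitative from 0 to 100%. The one yes/no indicator is the treatment itself, with the negative code "No= Did not apply". No row records a harm.
- **Elimination criteria.** The list includes "Patients who present an allergic or infectious reaction related to hyaluronic acid or prolotherapy or sepsis and antisepsis methods for infiltration" and also "Patients who did not have complete follow-up during the study". The term elimination is not defined.
- **Sample Size.** The formula uses "p (probability to occur the studied event" without naming the event. The limits are stated separately: "The lower limit will be 60 participants and the higher limit will be 120 participants".
- **After treatment Group.** Once baseline scores are recorded, "two doses of Hyaluronic Acid plus sorbitol will be applied". No uninjected participants are described. Scores are then recorded at 15 days, 3 months and 6 months.
- **Statistical analysis.** This section covers the functional scores, then relative risk, attributable risk and Fisher's test. It names neither an event nor a safety analysis.
- **Introduction, on hyaluronic acid infiltration.** Injection pain and a feeling of heaviness are named as possible effects. Neither is in itself an elimination ground, and neither has a row in the table.

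**The concern.** The allergic or infectious reaction is the only product- or procedure-related harm that the methods name, and the methods name it only as a reason for elimination. A stated rule, followed literally, would take out of the analysed set the very people whose experience answers the safety objective. If the safety statement is then drawn from the analysed set, the study could report a clean result that it did not observe. The issue is who is counted. It does not bear on how a participant with a reaction is managed or followed.

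**Working it through.** **Step 1: how elimination can be read.** The list mixes ordinary withdrawals, such as a participant's wish to leave, with incomplete follow-up. Incomplete follow-up can be established only once follow-up has failed or ended, so that criterion must act on who is analysed rather than on who enters. The reaction criterion stands in the same list under the same word. No sentence says that eliminated participants stay in a safety count.

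**Step 2: consequence on that reading.** Let n be the number injected and k the number with a reaction. The documents give no safety figure to reproduce.

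- n = 60 and n = 120 come from the Sample Size limits, assuming that everyone enrolled is injected.
- k is assumed, because the documents give no reaction rate. A range is shown.
- Reactions are taken as the only reason for elimination. Other eliminations would shrink the kept denominator and leave its reaction count at zero.

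Formulas, with exact (Clopper-Pearson) two-sided 95% limits:

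- Kept set: 0/(n − k), upper limit 1 − 0.025^(1/(n − k)).
- All injected: k/n, with lower limit the 0.025 quantile of Beta(k, n − k + 1) and upper limit the 0.975 quantile of Beta(k + 1, n − k).

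Example with n = 60 and k = 6: the kept set is 0/54, with upper limit 1 − 0.025^(1/54) = 6.6%. All injected is 6/60 = 10.0%, with limits 3.8% and 20.5%.

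| Injected | Reactions (assumed) | Kept set | All injected (95% CI) |
|---|---|---|---|
| 60 | 1 | 0/59, upper 6.1% | 1.7% (0.04 to 8.9) |
| 60 | 3 | 0/57, upper 6.3% | 5.0% (1.0 to 13.9) |
| 60 | 6 | 0/54, upper 6.6% | 10.0% (3.8 to 20.5) |
| 120 | 3 | 0/117, upper 3.1% | 2.5% (0.5 to 7.1) |
| 120 | 6 | 0/114, upper 3.2% | 5.0% (1.9 to 10.6) |

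With 6 reactions, in 60 or in 120, the kept-set upper limit lies below the rate actually seen. With the smaller counts it does not, but the point estimate is still 0%. If no reaction occurs, the two analyses agree: 0/60 has upper limit 6.0% and 0/120 has 3.0%.

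**Step 3: could the choice of set matter at low rates?** The chance of at least one reaction is 1 − (1 − r)^n. At an assumed true rate r of 1% it is 45% for n = 60 and 70% for n = 120. At 2% it is 70% and 91%.

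**Step 4: the risk measures.** Relative risk, attributable risk and Fisher's test need a yes/no outcome and two groups. The variable table has no yes/no outcome, and no participant is described as uninjected. As written, they cannot compare treated with untreated.

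**The case against.** The strongest reply is that the documents never say a reaction rate will be computed among those kept. The list can equally be read as a withdrawal list whose reasons are reported, in which case each reaction would appear as a reason for leaving. That stands: the 0% is conditional, and it is trivially true of any group selected for not having the event. What remains is that the text does not settle the reading and plans no safety analysis under either one.

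A reader might go further in four ways that the documents do not support.

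- **That every safety rate would be 0%.** Only the named reactions are affected. Injection pain and heaviness are not elimination grounds in themselves.
- **That the plan has nothing that could serve as its event.** The Hypothesis section speaks of 'Good' results, which could be made yes/no. What is missing is the score cut-off.
- **That 60 to 120 is wrong because the formula is left without values.** The text does not say that the limits come from the formula, and ordinary inputs fall inside them. At 95% confidence and an error of 10 points, p = 0.8 gives 1.96² × 0.16/0.01, rounded up to 62, and p = 0.5 gives 1.96² × 0.25/0.01, rounded up to 97.
- **That harms are recorded nowhere.** The data collection sheet breaks off at its treatment part in the text available, so the absence can be stated only for the variable table and the statistical section.

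It is also fair that reaction rates of 5% or 10% have no support in the documents, which describe the procedure as safe. They are illustrations.

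**Conclusion.** The point holds in conditional form. Safety is an objective without a listed variable or a stated analysis, and the only injection-related harm named in the methods is a ground for elimination. If only those kept are analysed, the rate of allergic or infectious reactions is 0% whatever happened. The size depends on how many reactions occur, which the documents do not give. Over the assumed counts, the rate in all injected runs from 1.7% to 10.0%, against 0% in the kept set. With no reactions nothing is lost.

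The conclusion rests on reading elimination as removal from analysis, which the follow-up criterion supports but the text does not state. It should be corrected, because it concerns one of the two stated aims and the remedy is cheap. It can still be made after enrolment (the document is dated 01/12/2023 and the population window is June to October 2022), because it changes who is counted and not who is recruited.

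**What to change.** 1. **Variable table.** Add a row: *Allergic or infectious reaction attributed to the infiltration: yes/no.* List any other injection-related effect that is recorded, such as pain or heaviness.
2. **Statistical analysis.** Add: *Safety is analysed in all injected participants, including those eliminated from the score analysis. The rate is participants with a reaction divided by participants injected, one count per participant, over a stated window (for example, to the last recorded contact), with an exact (Clopper-Pearson) 95% CI. The number whose reaction status is unknown is reported, and the rate is also given among those with known status.*
   The window and the unknown-status rule are needed because the first scheduled recording is at 15 days. Someone lost before then would otherwise be counted silently as reaction-free. For example, with an assumed 3 reactions in 60 injected and 6 of unknown status, the rate is 3/60 = 5.0% over all injected and 3/54 = 5.6% among those with known status.
3. **Risk measures.** Do not use relative risk, attributable risk or Fisher's test for before versus after or for treated versus untreated. If the intended event is a 'Good' result, state its KOOS or IKDC cut-off.

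**Cost.** One or more table rows and a few sentences, with no extra participants or visits. A reaction has to be recognised before the elimination rule can be applied, so the count should be recoverable. However, the documents do not describe how reactions are ascertained, and details for eliminated participants may have to be retrieved. The reported rate can only rise from 0%, and its interval will be wide with few events.
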